9.10.10. Electrocardiograms (ECG)

A 12-lead ECG will be recorded as indicated in [Table 3](#) after the patient has rested for at least 10 minutes in a supine position. The heart rate from the ECG machine should not be used as part of the vital sign measurements.

9.10.11. Vital Sign Measurements

Vital sign measurements include the patient's heart rate (beats/minute taken for at least 15 seconds), respiration rate, and body temperature. Blood pressure should be taken after the patient has rested in a sitting position for at least 5 minutes. The same arm (usually the non-dominant arm) and the appropriate size cuff should be used for each measurement. Vital sign measurements should be taken as indicated in [Table 3](#).

9.10.12. Physical Examination

A comprehensive physical examination must be performed by a physician, physician assistant, or registered nurse practitioner as indicated in [Table 3](#) and as documented within the table footnotes. The examination must include the following organ or body system assessments: head, eyes, ears, nose, throat, musculoskeletal, cardiovascular, lymphatic, respiratory, abdomen, skin, extremities, and neurological. Assessments of any specific signs or symptoms reported by the patient must also be performed and documented along with any other findings of note. Findings at Screening must be characterized as either normal or abnormal; if abnormal, a description of the abnormality must be provided. Following the examination at Screening, changes must be

classified as new, worsened, or improved from the last time the body system was assessed. If possible, the same individual should perform each physical examination on a patient during the study.

9.10.13. Pulmonary Function Testing

Pulmonary function testing that includes forced vital capacity (FVC), FVC percent predicted (FVC%), forced expiratory volume in 1 second (FEV1), FEV1 percent predicted (FEV1%), FEV1/FVC ratio, peak expiratory flow (PEF), and total lung capacity (TLC), must be performed as indicated in [Table 3](#).

9.10.14. Ventilation-Perfusion (V/Q) Lung Scan, Spiral/Helical/Electron Beam Computed Tomography (CT) or Pulmonary Angiogram

Ventilation-perfusion (V/Q) lung scan, spiral/helical/electron beam computed tomography (CT) or pulmonary angiogram are required to determine eligibility. If this assessment has not been previously performed for a patient, it must be performed at Screening. If V/Q scan is abnormal at Screening (*i.e.*, results other than normal or low probability), then a confirmatory CT or selective pulmonary angiography must be performed at Screening to exclude chronic thromboembolic pulmonary hypertension (CTEPH).

9.10.15. Right Heart Catheterization

A right heart catheterization (RHC) completed within 36 months of Day 1 is required. However, if a patient has not had a RHC completed within 36 months of planned Day 1, it should be performed after the patient has signed Informed Consent and has passed the Screening eligibility procedures.

In addition, data resulting from a RHC performed within 36 months before Day 1 or during the course of the study as part of the patient's standard of care should be collected on the patient's case report form. Other data resulting from procedures conducted as part of the standard of care for the patient that may contribute to the Sponsor's understanding of the safety or efficacy of the compound may also be requested.

9.10.16. Pregnancy Test

WOCBP (see [Section 9.8](#)) will complete a pregnancy test as indicated in [Table 3](#), or at any time if pregnancy is suspected. Negative test results are required on Day 1 before study drug administration. Any patient who becomes pregnant during the study must discontinue taking study drug immediately. See [Section 9.8.3](#) for a description of procedures to be followed in case of pregnancy.

9.10.17. Study Drug Administration

Patients should self-administer one capsule from each bottle included in the study drug kit orally once a day, preferably in the morning, as indicated in [Table 3](#). On days when PK samples are

collected, patients must not self-administer study drug. Study staff will administer study drug at the clinic following collection of the first PK sample.

At the Week 24 visit, patients who opt to participate in a sub-study of 24-hr PK must not administer study drug before either day of the Week 24 visit. On the second day of the Week 24 visit, patients must administer study drug after the 24-hr PK blood collection has been performed.

A vomited dose must not be replaced. A double dose (*e.g.*, missed dose from previous day and dose for current day) must not be taken.

9.10.18. Study Drug Dispensation and Collection

Study drug will be dispensed to the patient and collected from the patient as indicated in [Table 3](#). The patient will be dispensed one treatment kit at Day 1 and Week 4; two treatment kits will be dispensed at Week 8 and Week 16. Dispensed treatment kits from each visit should be returned to the site for collection at the subsequent visit.

9.10.19. Telephone Contact

Patients will be contacted by telephone as indicated in [Table 3](#). Patients will be asked about their body weight and other signs of fluid retention, as well as adverse events and any changes to concomitant medications. If fluid retention is suspected, the patient must be brought into the clinic and evaluated by the investigator as soon as possible, as detailed in [Section 9.1.1](#).

9.10.20. Adverse Event Collection

Patients will be observed for general appearance, presence of illness or injury, or signs indicative of a concurrent illness as indicated in [Table 3](#). Patients must be instructed to volunteer any information regarding AEs on or after the first dose of study drug or query the patients with an open question regarding any AEs they may be experiencing (*e.g.*, “How have you been feeling since your last visit?”). Any findings are to be documented. Patients must be asked if they have been hospitalized, had any accidents, used any new medications, or changed concomitant medication regimens (including prescription drugs, over-the-counter medications, vitamins, herbal products, and minerals). Responses must be documented in the source documents.

9.10.21. Clinical Chemistry

Samples will be collected for the following clinical chemistry analyses as indicated in [Table 3](#): ferritin, creatine kinase (CK), blood urea nitrogen (BUN), creatinine, total bilirubin, direct bilirubin, alanine aminotransferase (ALT), aspartate aminotransferase (AST), alkaline phosphatase (ALP), sodium, potassium, calcium, phosphorus, uric acid, total protein, glucose, albumin, lactate dehydrogenase (LDH), magnesium, chloride, bicarbonate, gamma-glutamyl transpeptidase (GGT). Women of child-bearing potential will require a serum pregnancy test (hCG-Qual) at Screening or at any point in time if a pregnancy is suspected.

9.10.22. N-Terminal Pro-Brain Natriuretic Peptide (NT-Pro BNP) and Brain Natriuretic Peptide (BNP)

Samples will be collected for NT-Pro BNP and BNP as indicated in [Table 3](#). As recent exercise may affect BNP and NT-Pro BNP levels, patients must be allowed to rest for a minimum period

of one hour following arrival at the clinic and prior to obtaining this blood sample. Similarly, this sample must be taken prior to the 6MWT or at least one hour after 6MWT. This sample must be taken with the patient in the same position at all appropriate visits, *e.g.*, sitting or semi-recumbent.

Detailed instructions on collection, storage and shipment of the sample will be provided in the central laboratory manual provided to the investigator.

9.10.23. Hematology

Samples will be collected for the following hematology assessments as indicated in [Table 3](#): hematocrit, hemoglobin, red blood cell (RBC) count, white blood cell (WBC) count, neutrophils, bands (if detected), lymphocytes, monocytes, basophils (if detected), eosinophils (if detected), absolute platelet count, mean corpuscular hemoglobin (MCH), mean corpuscular volume (MCV), and mean corpuscular hemoglobin concentration (MCHC).

9.10.24. Urinalysis and Microscopy

Samples will be collected for the following urinalysis and microscopy assessments as indicated in [Table 3](#): specific gravity, ketones, pH, protein, blood, glucose, clarity, color, leukocytes, nitrite, bilirubin, and a microscopic examination (if indicated based on laboratory results).

9.10.25. Virus Serology

Blood samples will be collected for testing for hepatitis B and hepatitis C as indicated in [Table 3](#). If the initial hepatitis C result is positive, then the patient will need to return for an unscheduled HCV RNA assessment to determine if the virus is present at the current time. If the results of this test are negative, the patient may continue in the Screening process.

9.10.26. 6-Minute Walk Test

A 6-minute walk test (6MWT) will be administered to patients as indicated in [Table 3](#). Unless otherwise indicated as described below, each test must be performed in strict accordance with the American Thoracic Society (ATS) guidelines [[ATS Statement 2002](#)] provided in [Section 19 Appendix 1](#). The appropriate language version will be applied for patients with a non-English informed consent. The walking course must be 30 m in length, except at sites granted prior sponsor agreement.

Determination of eligibility for 6MWD is based on the 6MWTs performed on separate days at Screening and Day 1. If a Screen B 6MWT is performed, 6MWD eligibility is based on the Screen B and Day 1 6MWDs. Otherwise, 6MWD eligibility is based on the Screen A and Day 1 6MWDs.

The two 6MWD values used to determine eligibility must have a percent difference $\leq 15\%$, as determined by the following calculation:

$$\text{Percent Difference} = |X-Y| / ((X+Y)/2)$$

$$X = 1^{\text{st}} \text{ 6MWD value (Screen A or Screen B)}$$

$$Y = 2^{\text{nd}} \text{ 6MWD value (Day 1)}$$

$$|X-Y| = \text{absolute value of the difference between the two 6MWD values}$$

[REDACTED]

The assessor of the 6MWT must not provide the patient with the results of the assessment once complete. A patient should wear the same shoes for all 6MWTs. Additionally, if a patient uses a walking aide for the first test, this same aide should be used during all subsequent tests. The shoes worn and walking aid used for each 6MWT should be noted in source documents.

Patients who require supplemental oxygen with exercise may use their prescribed oxygen level during 6MWTs. The oxygen level administered during Screening should be used during all subsequent tests. Titration of supplemental oxygen levels used during the 6MWT should only occur during the Screening Visit 6MWT via the site’s standard oxygen titration/administration processes. If a patient’s health status deteriorates during study participation and it is determined by a physician that the patient requires additional supplemental oxygen, the patient may continue study participation. However, the original supplemental oxygen level used during the Screening Visit 6MWT should continue to be used during all subsequent 6MWTs. In the opinion of the investigator, if a patient’s health status deteriorates to the point that the patient can no longer safely conduct subsequent 6MWTs using the original supplemental oxygen set at the Screening Visit, then 6MWT should not be conducted.

9.10.27. [REDACTED]

[REDACTED]

9.10.28. Quality of Life

[REDACTED]

9.10.29. WHO/NYHA Functional Class Assessment

WHO/NYHA functional class will be assessed ([Section 20, Appendix 2](#)) as indicated in Table 3 [REDACTED] To the extent feasible, the same evaluator should assess WHO/NYHA FC for a particular patient over the entire course of the study. [REDACTED]

[REDACTED]

[REDACTED]

[REDACTED]

[REDACTED]

[REDACTED]

[REDACTED]

9.10.32. Pharmacokinetic (PK) Blood Samples

Blood samples for determination of plasma bardozone methyl and potential metabolite concentrations will be drawn as indicated in Table 3. Patients must be instructed to not take their study drug prior to coming to the clinic for visits when PK samples will be collected. Patients will be asked by site personnel to provide the time of their last two administrations of study drug prior to the blood samples being collected. Blood sample collection instructions should be referenced in the laboratory manual.

The date and time of collection of all PK blood samples should be recorded; however, any deviations from the protocol-specified sampling times will not be considered protocol deviations. Sample time deviations will be summarized in the study report. Dates in the case report form should be recorded in an unambiguous format (*e.g.*, DD MMM YYYY) and time should be recorded to the nearest minute (*e.g.*, HH:MM using the 24-hour clock). Blood samples not drawn should be recorded as such.

Patients may participate in an optional PK sub-study, which will involve additional PK blood draws prior to dosing and 1, 2, 3, 4, 6, 8, and 24 hours after dose administration during the 2-day Week 24 visit. Patients who participate in the PK sub-study will also have PK blood draws collected during the Week 8 visit as indicated in Table 3. Patients not participating in the PK sub-study may have blood collected on either day of the Week 24 visit.

10. STUDY DRUG MATERIALS AND MANAGEMENT

10.1. Study Drug

Bardoxolone methyl capsules, 2.5 mg and 5 mg, will be used in this study.

10.2. Study Drug Packaging and Labeling

The study drug will be supplied in tamper-evident kits containing two 30-cc high-density polyethylene (HDPE) bottles. Each bottle will utilize foil induction-seal liners and a child-resistant closure. Each bottle of study drug will contain 30 capsules of 2.5 mg or 5 mg strength bardoxolone methyl or the matching placebo capsules. Each bottle will also contain a desiccant insert that must not be ingested. Labeling on each kit bottle will contain at minimum the following information:

- Medication ID number;
- Protocol 402-C-1504;
- Caution Statement: New Drug – Limited by Federal Law to Investigational Use. Keep out of sight and reach of children;
- Control or lot number
- Store at 20° – 25°C (68° – 77°F), short term excursions allowed to 15° – 30°C (59° – 86°F);
- Reata Pharmaceuticals, Inc., Irving, TX.

A double panel label will be presented on the treatment kit carton containing this and other information as well. Additionally, labeling, in the relevant local languages for investigational medicinal product (IMP) for use and distribution in the EU shall adhere to current Eudralex, Volume 4 Annex 13 guidance and requirements.

10.3. Study Drug Storage

The stability of the drug product has been and is currently being evaluated in ongoing studies.

Investigative sites must store the investigational product in a secure location with room temperature conditions of 20° - 25°C (68° - 77°F), with brief excursions allowed to 15° – 30°C (59° – 86°F).

10.4. Study Drug Administration

Please refer to [Section 9.10.17](#) for details on study drug administration. Clear instructions will be provided to the patient regarding the number and type of capsules to be ingested at each study drug administration time point listed in [Table 3](#). Patients must be instructed to continue taking study drug once daily up through their Week 24 visits unless: (1) patient has been otherwise instructed by the investigator or (2) the patient has been formally discontinued from the study.

10.5. Study Drug Accountability

The investigator, or designee, will maintain a record of all study drug received, dispensed, and returned to the Sponsors' designee. No study drug shall be destroyed by the clinical site unless directed in writing to do so by the Sponsor's quality assurance department. Study drug bottles and any unused capsules should be returned to the study staff for eventual disposition by the Sponsor. The number of capsules returned at each visit will be recorded for each bottle in the kit.

10.6. Study Drug Handling and Disposal

At the conclusion of the study or in an instance of planned study drug replacement, the Sponsor or its designee will direct the site regarding the final disposition of study drug.

11. SAFETY ASSESSMENTS

11.1. Safety Parameters

To avoid inter-observer variability, every effort should be made to ensure that the same individual who made the initial baseline determinations completes all safety assessments. Safety parameters include vital sign measurements, ECG results, physical examination results, adverse events, serious adverse events, weight, and laboratory test results (clinical chemistry, hematology, urinalysis and microscopy).

11.2. Adverse and Serious Adverse Events

11.2.1. Definition of Adverse Events

11.2.1.1. Adverse Event

An adverse event (AE) is defined as any untoward medical occurrence in a patient regardless of its causal relationship to study drug. An AE can be any unfavorable and unintended sign (including any clinically significant abnormal laboratory test result), symptom, or disease temporally associated with the use of the study drug, whether or not it is considered to be study-drug related. Included in this definition are any newly-occurring events or previous condition that has increased in severity or frequency since the administration of study drug.

All AEs that are observed or reported by the patient during the study (from time of administration of the first dose at the Day 1 visit until the final visit indicated in [Table 3](#) must be reported, regardless of their relationship to study drug or their clinical significance.

11.2.1.2. Serious Adverse Event

A serious adverse event (SAE) is any AE occurring at any dose and regardless of causality that:

- Results in death;
- Is life-threatening;
- Requires inpatient hospitalization or prolongation of existing hospitalization;
- Results in persistent or significant incapacity or substantial disruption of the ability to conduct normal life functions;
- Is a congenital anomaly or birth defect in an offspring of a patient taking study drug;
- Is an important medical event.

The term "life-threatening" refers to an event in which the patient was at immediate risk of death at the time of the event. It does not refer to an event that hypothetically might have caused death if it were more severe.

Important medical events are those that may not meet any of the criteria defined above; however, they may be considered serious when, based upon appropriate medical judgment, they may

jeopardize the patient and may require medical or surgical intervention to prevent one of the other outcomes listed in the SAE definition.

Pregnancy is not considered an AE; however, information will be collected for any pregnancies that occur during the study (from the time of the first dose of study drug until the final visit indicated in [Table 3](#), as appropriate). Certain pregnancy outcomes will require submission as an SAE (See [Section 9.8](#)).

The investigator is responsible for reporting to Reata or designee all AEs and SAEs that are observed or reported by the patient during the study (from the time of administration of the first dose of study drug until the final visit indicated in [Table 3](#), as appropriate), regardless of their relationship to study drug or their clinical significance.

The Sponsor, or the Contract Research Organization (CRO) on the behalf of the Sponsor, must be notified immediately regarding the occurrence of any SAE that occurs after the patient is randomized and throughout the study, regardless of study drug administration, including SAEs resulting from protocol-associated procedures, as defined in relevant legislation. The procedures for reporting all SAEs, regardless of causal relationship, are as follows:

- Record the SAE on the AE eCRF and complete the “Serious Adverse Event Report” form within the electronic database.
- In the event the electronic database is not functional, a paper SAE form will be available for the reporting of SAEs.

The Sponsor may request additional information from the investigator to ensure the timely completion of accurate safety reports.

All SAEs reported or observed during the study must be followed to resolution or until the investigator deems the event to be chronic or the patient to be stable. Reata or designee may contact the investigator to obtain additional information on any SAE which has not resolved at the time the patient completes the study.

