11.6. Recording Adverse Events

All conditions present prior to the administration of the first dose of study drug (Day 1) should be documented as medical history. After the first dose, documentation of adverse events (AEs) shall continue until 28 days following administration of the final dose of study medication, regardless of the relationship of the AE to study drug. Information to be collected includes type of event, date of onset, date of resolution, investigator-specified assessment of severity and relationship to study drug, seriousness, as well as any action taken.

While an AE is ongoing, changes in the severity (*e.g.*, worsening and improving) should be noted in the source documents, but when documenting the AE, only the total duration and

greatest severity should be recorded in the eCRF. AEs characterized as intermittent require documentation of onset and duration.

All drug-related (possibly, probably, or definitely related, see [Section 11.4](#)) AEs and abnormal laboratory test results reported or observed during the study must be followed to resolution (either return to baseline or within normal limits). All other AEs will be followed through the final visit indicated in [Table 3](#), as appropriate.

AEs resulting from concurrent illnesses, reactions to concurrent illnesses, reactions to concurrent medications, or progression of disease states must also be reported. Preexisting conditions (present before the start of the AE collection period) are considered concurrent medical conditions and should NOT be recorded as AEs. However, if the patient experiences a worsening or complication of such a concurrent condition, the worsening or complication should be recorded as an AE. Investigators should ensure that the AE term recorded captures the change in the condition (*e.g.*, “worsening of...”). Any improvement in condition should be documented per [Section 9.10.12](#).

[figure not shown]

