16.2. Case Report Forms

All case report form data will be entered in paper or electronic forms at the investigational site. A 21 CFR Part 11 compliant Electronic Data Capture system (EDC) will be used to capture data electronically for all randomized patients.

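### A serious complication of a catheterization, CT or angiogram that the protocol requires before Day 1 falls ahead of both SAE start points, so it has no defined SAE report to the sponsor

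*Protocol*

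**What the plan says.** **Start of reporting.** Protocol 11.2.1.2 gives two start points. One paragraph makes the investigator responsible for reporting AEs and SAEs "from the time of administration of the first dose of study drug until the final visit indicated in" Table 3. The next requires immediate notification to the sponsor or CRO of "any SAE that occurs after the patient is randomized and throughout the study, regardless of study drug administration, including SAEs resulting from protocol-associated procedures". Section 11.2.1.1 sets the AE window as "from time of administration of the first dose at the Day 1 visit until the final visit indicated in" Table 3. Section 11.7 gives 24 hours for an SAE report, through the clinical database.

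**Procedures before that.** Section 9.10.15 covers the patient with no right heart catheterization within 36 months of planned Day 1: "it should be performed after the patient has signed Informed Consent and has passed the Screening eligibility procedures". Section 9.10.14 requires a V/Q scan, CT or pulmonary angiogram at Screening if none has been done. After an abnormal V/Q scan, "a confirmatory CT or selective pulmonary angiography must be performed at Screening".

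**Handling of earlier events.** Section 11.6 says: "All conditions present prior to the administration of the first dose of study drug (Day 1) should be documented as medical history". Section 16.2 says that the electronic system "will be used to capture data electronically for all randomized patients", although its preceding sentence allows paper forms as well. SAP 12.1 starts the safety analyses at randomization and limits them to the safety population, which SAP 3.2 defines as patients who took at least one dose.

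**The concern.** The notification clause is meant to catch harm from the trial's own procedures, whether or not the patient has taken study drug. Its start date, however, leaves out the catheterization and angiography that the protocol itself can order, because both are done during Screening.

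The result is uneven. Section 9.10.15 foresees a standard-of-care catheterization during the study. A serious complication of that one, after dosing, would be reportable. The same complication of a catheterization done only to qualify the patient for the trial would not be.

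What is at stake is oversight of harm that the trial may cause. The sponsor's SAE process and the DSMB could lack a timely, structured report, with causality assessment and follow-up, of a serious event brought about by an eligibility procedure. The efficacy results are not affected.

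**Working it through.** No calculation decides this point. The check puts the start dates and the procedures in order and then follows one event through each recording route.

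**1. Order of events**

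| Step | Source | SAE window open? |
|---|---|---|
| Informed consent | Protocol 9.10.1 | No |
| Screening, up to 90 days | Table 3, footnote a | No |
| Imaging (V/Q, CT or angiogram) if none exists; confirmatory CT or angiography if V/Q abnormal | Table 3, footnote j; 9.10.14 | No |
| Catheterization if none within 36 months, after the other screening checks | 9.10.15 | No |
| Randomization on Day 1 | 9.10.2 | Sponsor notification opens (11.2.1.2) |
| First dose on Day 1 | Table 3, footnote c | Investigator AE and SAE reporting opens (11.2.1.1, 11.2.1.2) |
| Day 1 AE assessment, after dosing | Table 3, footnote l | Open |

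Table 3 marks no AE collection at Screen A or Screen B. Whichever start point is used, the required catheterization and imaging lie before it.

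**2. One serious complication, followed through the routes**

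- *Patient recovers and is dosed.* Section 11.6 sends the event to medical history. That entry carries no 24-hour deadline, seriousness flag or causality assessment. Only a worsening after first dose would count as an AE. The event itself precedes the SAP 12.1 window and is not treatment-emergent under SAP 12.2.
- *Patient fails screening or dies before randomization.* Sections 11.2.1.1 and 11.2.1.2 do not reach the event. Section 16.2 describes electronic capture for randomized patients, and 11.2.1.2 and 11.7 offer the paper SAE form only for when the database is down. The patient is not in the safety population. What remains is the investigator's duty in 11.7 to tell the IRB/EC of SAEs at the site and copy that correspondence to the sponsor, and the duty in 15.5 to tell the IRB/EC of problems involving risk to patients.

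**3. The two start points**

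The two paragraphs in 11.2.1.2 also differ for an SAE of any cause between randomization and first dose. Sponsor notification covers it; investigator reporting, as dated in the paragraph before, does not.

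**4. Number exposed**

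The documents do not say how many patients would lack a catheterization within 36 months or prior imaging. As an illustration only, suppose 10% to 30% of about 130 enrolled patients needed a new catheterization: 0.10 × 130 = 13 and 0.30 × 130 = 39, with screen failures on top. This range is an assumption with no basis in the documents, and the conclusion does not depend on it.

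**The case against.** The strongest reply is that such an event does not vanish. Section 11.7 tells principal investigators to inform the IRB/EC of SAEs at their site and to send SAE correspondence to the sponsor for the study file. Neither sentence has a start date or is limited to randomized patients. Section 15.5 adds the duty on risks to patients. Section 11.3 has patients asked about their health at every study visit, with answers kept in source documents. Section 16.2 allows paper forms. A reader might infer that a screening harm is never recorded anywhere, or that no ethics committee would hear of it. The text does not support that.

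A reader might also infer that every procedure capable of serious harm precedes randomization, which would leave the procedural clause almost empty. That is not supported either. Walk tests continue at Weeks 4, 8, 16, 24 (twice) and 28. Appendix 1 mentions arrhythmia or cardiovascular collapse as a possible risk in some patients, while noting thousands of tests without serious events. Laboratory draws and serial PK sampling (9.10.32) also follow randomization. Several Table 3 rows are redacted, so no complete list of later procedures can be made. Nor do the documents say that the CT uses contrast.

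Finally, both procedures are conditional: catheterization only if none is recent enough, and angiography as one of several imaging options.

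All of this stands and limits the point. It does not remove it. The 11.7 duty works only if a site treats as an SAE something that 11.2.1.1, 11.2.1.2 and 11.6 place outside the window. Correspondence in the study file is not a 24-hour SAE report, and no route from it to the DSMB is described.

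**Conclusion.** The point holds in a limited form. For a catheterization, CT or angiogram that the protocol requires during Screening, a serious complication has no defined SAE report to the sponsor and does not enter the planned safety analyses, although 11.2.1.2 names procedure-related SAEs as notifiable. For a patient who is never randomized, only the general duties in 11.7 and 15.5 remain. Procedural events after randomization are covered.

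The size is unknown: an uncounted and possibly small number of patients, over a Screening period of up to 90 days. No efficacy or TEAE result depends on it. The change is worth making because it concerns harm from the trial's own procedures and costs little.

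This rests on reading the start points literally, and on there being no consent-based SAE rule in redacted text or in a separate safety manual that the documents do not show.

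**What to change.** Make one short protocol amendment:

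- **11.2.1.2:** reconcile the first-dose and randomization start points into one stated start for SAE reporting in general.
- **11.2.1.2 and 11.7:** for SAEs attributed to a protocol-required procedure, start reporting at informed consent, with screen failures included and the existing 24-hour limit applied.
- **11.6:** exempt these events from the rule that sends pre-dose conditions to medical history.
- **11.7 and 16.2:** make the SAE form, in the database or on paper, available for consented patients who are not randomized.
- **SAP 12.2:** leave the TEAE definition as it is and add a separate listing of pre-dose procedural SAEs, including those in patients outside the safety population.

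The cost is the amendment, form access for screened patients and a few extra SAE reports. General AE collection can stay at first dose, and no efficacy or TEAE analysis changes.
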